2.8.3.2 Other special lab results

Other non-routine laboratory data include pregnancy test results, CD19⁺B-cell counts, CD3⁺, CD20⁺T-cell counts, total IgG, total IgM, [REDACTED]. All data will be listed appropriately.

The B-cell counts, T-cell counts, total IgG, total IgM, [REDACTED] will be summarized using descriptive statistics by treatment group and visit-window.

In addition, number and percentage of patients with B-cells < the lower limit of normal (LLN) will be presented by treatment group and visit-window. Graphic presentation of B-cell counts distribution via box-plots will also be provided by treatment group and visit-window.

Number and percentage of patients meeting the notable low level criteria in IgG or IgM at least once will be provided by treatment group. A notably low IgG level is defined as a level that is 20% below the LLN and a notably low IgM level is defined as a level 10% below the LLN.

The following analyses will be repeated for Cut-off 2 analysis:

- Number and percentage of patients with B-cells < LLN by visit window
- Number and percentage of patients meeting the notable low level criteria in IgG and IgM
- Summary statistics

2.8.4 Other safety data

2.8.4.1 ECG

ECG data will be collected at baseline visit, Week 24 visit, Week 48 visit, and EOS visit. Clinically significant findings from ECG evaluations will be reported as AEs and included in

the analysis of AEs. ECG parameters include max heart rate, mean PR duration, mean QT duration, mean QRS duration, and QT corrected using Fridericia's correction formula (all as collected on the ECG CRF). Descriptive statistics of each ECG parameter will be provided by treatment group for baseline and for the 3 nominal visits (i.e., Week 24, Week 48, and EOS visits).

The number and percentage of patients meeting the criteria defined in [Table 2-13](#) will be provided for each criterion by treatment group for baseline and for the 2 nominal visits.

Table 2-13 Criteria for relevant ECG absolute or change from baseline values

Absolute values criteria:	Changes from baseline criteria:
Heart rate: HR<40 or HR>120 beats/min	QRS complex: increase>25% compared to baseline
Pulse rate: PR<110 or PR>200 msec	QTcF > 500 msec and QTcF increase > 60 msec
QRS complex =: <70 msec or >120 msec	
QTcF <350 or >450 msec (males)	
QTcF <360 or >460 msec (females)	

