Highly immunosuppressive/chemotherapeutic medications (mitoxantrone, cyclophosphamide, cladribine) B-cell targeted therapies such as rituximab, ocrelizumab Laquinimod	2 years prior to randomization
Mitoxantrone (with evidence of cardiotoxicity following treatment or cumulative life-time dose $> 60 \text{ mg/m}^2$) Alemtuzumab Lymphoid irradiation; bone marrow transplantation Other strongly immunosuppressive treatments (with effects potentially lasting over 6 months) Ofatumumab	Any time

13. Use of other investigational drugs at the time of enrolment (Screening) or within the prior 30 days, or five elimination half-lives, or until the expected pharmacodynamic effect has returned to baseline, whichever is longer
14. History of malignancy of any organ system (other than basal cell carcinoma, *in situ* squamous cell carcinoma of skin, or *in situ* carcinoma of cervix of the uterus that have been radically treated e.g. completely excised with clear margins), within the past 5 years, regardless of whether or not there is evidence of local recurrence or metastases
15. Any of the following conditions or treatments that may impact the safety of the patient:
 - Cardiac or cardiac repolarization abnormality, including any of the following:
 - History of myocardial infarction (MI), angina pectoris, or coronary artery bypass graft (CABG) within 6 months prior to starting study treatment
 - Clinically significant cardiac arrhythmias (e.g., ventricular tachycardia), complete left bundle branch block, high-grade atrioventricular (AV) block (e.g., bifascicular block, Mobitz type II and third degree AV block)
 - Resting the Fridericia QT correction formula ($\text{QTcF} \geq 450 \text{ msec}$ (male) or $\geq 460 \text{ msec}$ (female) at pretreatment (screening or baseline) or inability to determine the QTcF interval
 - Risk factors for Torsades de Point including uncorrected hypokalemia or hypomagnesemia, history of cardiac failure, or history of clinically significant/symptomatic bradycardia or any of the following:
 - Long QT syndrome, family history of idiopathic sudden death or congenital long QT syndrome
 - Concomitant medication(s) with a “Known Risk of Torsades de Point” that cannot be discontinued or replaced by safe alternative medication.
 - History of or active severe respiratory disease, including Chronic Obstructive Pulmonary Disease, interstitial lung disease or pulmonary fibrosis
 - Patients with asthma requiring regular treatment with oral steroids

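### SAP Table 2-13's only QTcF change criterion, read literally, is one joint condition that counts no rise above 60 msec ending at or below 500 msec

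*SAP*

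**What the plan says.** SAP section 2.8.4.1 (ECG) plans three things for QTcF.

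- **Counts against Table 2-13.** The absolute column flags QTcF below 350 or above 450 msec in men, and below 360 or above 460 msec in women. The change-from-baseline column has two entries: a QRS increase of more than 25%, which stands alone, and for QTcF "QTcF > 500 msec and QTcF increase > 60 msec". Numbers and percentages of patients "will be provided for each criterion by treatment group for baseline and for the 2 nominal visits".
- **Summary statistics.** "Descriptive statistics of each ECG parameter will be provided by treatment group for baseline and for the 3 nominal visits". No summary of ECG change from baseline is stated. Laboratory data (SAP 2.8.3) and vital signs (SAP 2.8.4.2) each have one.
- **Adverse events.** "Clinically significant findings from ECG evaluations will be reported as AEs and included in" the adverse event analysis.

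Protocol section 4.2 bounds QTcF at entry. It excludes men at or above 450 msec and women at or above 460 msec "at pretreatment (screening or baseline) or inability to determine the QTcF interval".

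**The concern.** A change-from-baseline criterion is there to show how many patients moved by a notable amount. The QTcF entry joins a change to an absolute value with 'and', and counts are promised per criterion, so the literal output is one joint count. A patient can then have a rise well above the SAP's own 60 msec threshold and not be counted as having changed, because the end value did not pass 500 msec. A patient can also pass 500 msec and be left out of the row because the rise was too small.

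At stake is whether the ECG safety table reports what its two thresholds suggest. Two programmers could also read the line differently and produce different tables. No hypothesis test depends on it.

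**Working it through.** The plan states no figure to reproduce; this is a logical check with a small enumeration. Let b be baseline QTcF and p post-baseline QTcF, in msec. The limits are those of Table 2-13.

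- Absolute criterion A: p < 350 or p > 450 (men); p < 360 or p > 460 (women).
- Joint criterion J, the literal reading: p > 500 and p − b > 60.

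**1. Rises ending inside the absolute limits.** If p is at most 450 (men) or 460 (women), J fails whatever the rise, and A fails unless p is below the lower limit. With a baseline inside the limits, the largest rise that meets neither is 450 − 350 = 100 msec in men and 460 − 360 = 100 msec in women.

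**2. Rises ending between the upper limit and 500 msec.** A is met and J is not. The patient is counted as above 450 or 460 msec, with nothing to show the size of the change.

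**3. Values above 500 msec with a rise of 60 msec or less.** This needs b ≥ p − 60 > 440. Under the entry criteria that means whole-number baselines of 441 to 449 (men) or 441 to 459 (women). For any b ≤ 440, p > 500 already implies a rise above 60. The joint row is thus close to a count of values above 500 msec, with some of those values removed. It is not a count of rises.

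**4. Worked cases.**

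| Patient | Rise (msec) | A | J as written | Rise > 60 alone | > 500 alone |
|---|---|---|---|---|---|
| Man, 365 to 445 | 80 | no | no | yes | no |
| Woman, 395 to 458 | 63 | no | no | yes | no |
| Man, 400 to 495 | 95 | yes | no | yes | no |
| Woman, 455 to 505 | 50 | yes | no | no | yes |
| Man, 430 to 505 | 75 | yes | yes | yes | yes |

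**5. Enumeration.** Take whole-number pairs with b from an assumed 300 up to 449 (men) or 459 (women), and p from 300 to 600.

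- J holds in 150 × 100 − 45 = 14,955 pairs for men and 160 × 100 − 190 = 15,810 for women. The subtracted pairs are those of step 3: 9 + 8 + … + 1 = 45 and 19 + 18 + … + 1 = 190. None of the J pairs lies outside A, because 500 exceeds both 450 and 460.
- Rises above 60 msec that meet neither A nor J: 1 + 2 + … + 90 = 4,095 pairs for men and 1 + 2 + … + 100 = 5,050 for women. A separate rise row would count all of them.

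These pair counts show that the gap exists. They are not patient frequencies, which the documents give no means of estimating.

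**The case against.** The strongest objection is that 'and' here lists two criteria. The SAP uses the word loosely elsewhere. Section 2.8.3 lists patients with CTCAE grade 3 and 4 abnormalities, which cannot both apply to one result. Section 2.8.3.2 counts low IgG or IgM, then names the same analysis with 'and'. Where section 5.3.2 requires joint liver criteria, it uses an ampersand and adds a same-day rule. The QTcF line has neither, and it repeats the parameter name. On that reading the rise above 60 msec is already tabulated. This stands as a real possibility, but the SAP does not state it, and the literal wording gives one criterion.

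A reader might infer that the joint row is worthless because it identifies nobody whom the absolute limits miss. That does not follow. Criteria are counted separately, and nested tiers are ordinary practice: section 5.3.2 tabulates ALT above 3, 5, 10 and 20 times the upper limit. The joint row still isolates a severe subset. A stand-alone row above 500 msec would be nested in the same way.

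A reader might also infer that the table cannot detect change from baseline, or that large QTcF rises would stay hidden. The documents do not support this either. The QRS change rule works alone, and the joint row does catch some QTcF changes. QTcF statistics are given by visit, clinically significant findings become adverse events, and SAP 2.8 has all safety assessments summarized or listed as appropriate. These routes do not supply the missing count, however: by-visit summaries do not give the number of patients with a large individual rise, and the adverse event route depends on the investigator's judgement.

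Finally, the entry limits do not bound every baseline. For patients switching from placebo, SAP 2.1.1 sets the Cut-off 2 and final safety baseline at Week 24. That could widen the baseline range in step 3 but leaves the logic unchanged. No passage requires a stand-alone count of rises, so this is a point about clear reporting and not a breach of the plan.

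**Conclusion.** The point holds as a minor one. Taken literally, the single QTcF change criterion omits every rise above 60 msec that ends at or below 500 msec, including rises of up to 100 msec wholly inside the absolute limits. It also omits values above 500 msec reached by a rise of 60 msec or less. This rests on reading 'and' as joint. If two criteria were meant, the defect is ambiguous wording, and the same correction resolves it. How many patients would be affected cannot be determined from the documents. The consequence is confined to one descriptive safety table; the primary analysis, its significance level and its power are untouched.

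**What to change.** In Table 2-13, replace the joint QTcF line with two criteria, each tabulated on its own and using the SAP's existing thresholds:

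- QTcF > 500 msec, which serves as a severity tier within the absolute limits;
- QTcF increase > 60 msec from baseline, which is the row that finds patients the absolute limits miss.

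The rise row applies to post-baseline visits only. State that its denominator is patients with both a baseline and a post-baseline value, as the SAP already does for laboratory data and vital signs. The data are already collected, so the cost is one reworded table cell and one extra output row. This changes a reporting definition only and implies no change to patient management.

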2.8.4.2 Vital signs

Vital sign measurements and their change from baseline will be summarized with descriptive (mean, median, standard deviation, min, max) by visit window. The number and percentage of subjects with clinically notable vital signs will be presented.

Vital sign measurements include sitting systolic and diastolic blood pressure, sitting pulse, body temperature, height and body weight.

Three sitting measurements of blood pressure (SBP and DBP) and pulse will be taken at each vital sign assessment.

For post baseline assessments, the blood pressure and pulse values will be the average of the non-missing values of the 3 measurements. If more than one blood pressure/pulse assessment (scheduled or unscheduled) exists in a particular visit-window ([Section 2.1.2](#)) the blood pressure/pulse value will be the average of all assessments. Derivation of baselines for blood pressure and pulse are provided in [Section 2.1.1](#).

Height will be collected at screening visit only and will be summarized in the baseline characteristic summary only.

Analyses of vital sign measurements (excluding data collected on Day 1, Day 7, Day 14, Week 4 and Week 24) using descriptive summary statistics (mean, median, standard deviation, min, max) for the change from baseline for each post-baseline visit-window will be performed. These descriptive summaries will be presented by vital sign parameter and treatment group. Change from baseline will only be summarized for patients with both baseline and post-baseline values.

The number and percentage of patients with clinically notable vital signs will be presented. For clinical notable vital signs values, refer to [Section 5.4](#). This analysis will be repeated for Cut-off 2 analysis.

For vital signs data collected on Day 1, Day 7, Day 14, Week 4, and Week 24 protocol scheduled visit, pre and post-injection vital signs data including temperature, pulse rate and blood pressure are collected. Change from pre-injection to post-injection in these 3 parameters will be summarized by nominal visit. This analysis will be performed for Cut-off 1 analysis only.

2.8.4.3 Suicidality evaluations

In this study, the C-SSRS questionnaire will be administered electronically (eC-SSRS), via an interactive voice response (IVR) system. However, as per internal Novartis guidelines, a CRF page ‘Supplemental Data for Suicidal Ideation and Behavior Categories’ is also used as an unplanned/unscheduled visit for those cases when the subject did not conduct the interview because, e.g. the subject was hospitalized and unable to conduct the interview or the subject refused to conduct the interview/withdrew from the study and external information on suicidal ideation and behavior is required. In such cases, SIB information will still be collected from external parties (spouse, caregiver, nurse, investigator, etc.) through means of this CRF page. Further, for deaths due to suicide, the site should fill out the Supplemental Data CRF (“completed suicide” tickbox) to ensure accurate reporting of such cases. When reporting the SIB data, data from both sources (eC-SSRS and Supplemental CRF) will be used in a pooled manner and no distinction will be made between the two.

Definition of all prior history and recent history

SIB assessments obtained before the first dose of study drug will be defined by two components: *all prior history* and *recent history*.

All prior history will be defined as the SIB results obtained from the *lifetime* assessment, and *recent history* will be defined as the SIB results obtained from the assessment in past 6 months or past 24 months of the screening or baseline visit.

In case multiple assessments collected before first dose of study drug, results should be derived as the worst case value per the reporting timeframe. Worst case is defined by an answer ‘yes’ to the SIB category.

Data summary

SIB data will be summarized for the Safety Set. The number and percentage of subjects with suicidal ideation, suicidal behavior and self-injurious behavior without suicidal intent will be presented by analysis-period (recent history, all prior history and any time post-baseline) and treatment group. The following 4 types of events will be included in the summary table:

- Each of the 11 categories listed in [Table 2-14](#) separately
- Any suicidal ideation or behavior (a ‘yes’ answer to at least one of the 10 suicidal ideation and behavior questions in analysis-period of interest)
- Any suicidal ideation (answered ‘yes’ to at least one of the 5 suicidal ideation questions in analysis-period of interest)

- Any suicidal behavior (answered 'yes' to at least one of the 5 suicidal behavior questions in analysis-period of interest).

In addition, the number and percentage of subjects with the following post-baseline events will be presented (*Nilsson et al, 2013*):

Table 2-14 Standard SIB events

Category number	C-SSRS category
Suicidal Ideation	
1	Wish to be dead
2	Non-specific active suicidal thoughts
3	Active suicidal ideation with any methods (not plan) without intent to act
4	Active suicidal ideation with some intent to act, without specific plan
5	Active suicidal ideation with specific plan and intent
Suicidal behavior	
6	Preparatory acts or behavior
7	Aborted attempt
8	Interrupted attempt
9	Actual attempt
10	Completed suicide
	Self-injurious behavior, without suicidal intent
11	Non-suicidal self-injurious behavior

Note: in these definitions, a category of 0 is assigned to a subject without suicidal ideation (i.e. a 'no' answer to all suicidal ideation categories)

- Worsening suicidal ideation compared to recent history: An increase in the maximum suicidal ideation category at any time post-baseline from the maximum suicidal ideation category during pre-treatment recent history.
- Worsening serious suicidal ideation compared to recent history: An increase in the maximum suicidal ideation category to 4 or 5 at any time post-baseline from not having serious suicidal ideation (categories of 0-3) during pre-treatment recent history.
- Emergence of serious suicidal ideation compared to recent history: A maximum suicidal ideation category of 4 or 5 at any time post-baseline from no suicidal ideation (category 0) during pre-treatment recent history.
- Improvement in suicidal ideation at last on-treatment measurement compared to recent history: A decrease in suicidal ideation score at last on-treatment measurement from pre-treatment recent history.
- Emergence of suicidal behavior compared to all prior history: The occurrence of suicidal behavior (Categories 6-10) at any time post-baseline from not having suicidal behavior (Categories 6-10) prior to treatment (includes "lifetime" and any other assessments prior to treatment taken prior to treatment).

For those analyses, each subject can only be counted once for each event. However, a subject can be counted in several different events.

Suicidal ideation and behavior data will be listed. Detailed answers to C-SSRS items will be listed separately for subjects with any suicidal ideation at any time post-baseline (i.e. a 'yes' answer to at least one of the five suicidal ideation questions at any time post-baseline) and for a subject with any suicidal behavior at any time post-baseline (i.e. a 'yes' answer to at least one of the five suicidal behavior questions at any time post-baseline).

This analysis will be repeated for Cut-off 2 analysis with focusing on post-baseline.

2.8.4.4 Safety evaluation during the Safety follow-up

Safety data collected during the Safety Follow-up period includes adverse events, laboratory assessments (hematology, chemistry, urinalysis, B-cells, T-cells and Immunoglobulins) and eCSSRs. All safety assessments after study drug discontinuation will be analyzed, summarized or listed.

[figure not shown]
Safety data collected during the Safety Follow-up period will be reported separately. These analyses will include laboratory assessments including B-cell repletion, adverse events, vital signs, and eCSSRS. MS relapses and change in EDSS will also be collected. For all patients change is defined relative to the End of Study visit (EOS). Since post-treatment safety follow-up in the Safety Follow-up period may continue for up to 36 weeks (or longer if criteria for longer follow-up are met) after completion of the Treatment period study, the study report for the Core part (Screening and Double-blind treatment period) will be completed based on the completed core part i.e. based on all patients who have completed the Double-blind treatment period, and the partial data from the Safety Follow-up period available at that time. A complete analysis of the post-treatment safety follow-up will be provided in an addendum to the study report when all patients who entered the Safety Follow-up period have completed this period.

2.9 Pharmacokinetic endpoints

All completed subjects will be included in the pharmacokinetic (PK) data analysis. Concentrations will be given in mass per volume units. Missing values or those below the limit of quantification (LOQ) will be indicated in the data listings and treated as zero in data presentations and calculations. Pharmacokinetic parameters, expressed as mean, SD, and CV, with geometric means will be summarized.

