regimen of 3 separate 20 mg (at Day 1, 7 and 14) was required to attain target depletion (≤ 8 cells/ μ L) in $> 95\%$ of patients based on modeling, and is extrapolated to be more effective than a single 60 mg load. In Study OMS112831, patients dosed with 60 mg q4 weeks showed no signs of B-cell repletion during the inter-dosing interval. Based on PK/PD modeling, ofatumumab 20 mg sc appears to be sufficient to either maintain or to further deplete B-cells in $> 95\%$ of patients who have previously depleted, even in patients with high repletion rates.

High number of PK values below the lower limit of quantification (LLQ) did not allow for use of a full PK/PD modeling. For this reason, a second modeling approach (PK-PD) was used to relate the individual time-course of B-cells to the dosing history and patient specific covariates, taking the inter-patient variability into account. This approach also confirmed that the desired levels of B-cell depletion in nearly all patients can be attained through the described loading/maintenance dose regimen.

With regards to safety and tolerability, the dose regimens of 60 mg q12 and q4 weeks were associated with more AEs than the lower dose regimens of 3 mg or 30 mg q12 weeks. In particular, post injection systemic reactions reported as SAEs on Day 1 were seen only with the 60 mg dose regimens. In the presence of B-cells at first dosing, and when B-cells have started repleting, systemic reactions are an expected AE and their severity is likely to be dose and B-cell count related.

With regards to repletion of B-cells after discontinuation of ofatumumab, simulations based on a model developed using the data from the Phase 2 study (OMS112831) predict that the vast majority of patients will replete their B-cells within 9 months of follow-up. Based on these simulations it is estimated that around 5 months are needed to achieve 80% of repletion after treatment discontinuation.

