9.5.4 PK/PD

[figure not shown]
PK concentration and B-cell count data will be summarized by visit for the overall population, and separately by region (Japan or other countries) and provided together with by-patient listings in the study report.

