1.2 Study objectives and endpoints

Primary objective

The primary objective of the study is to demonstrate that ofatumumab is superior to placebo in reducing the cumulative number of Gd-enhanced T1 lesions across 4 MRI scans at Week 12, 16, 20 and 24 in patients with relapsing MS. The primary objective will be assessed during the core part. ([Section 2.5](#))

Secondary objectives

The secondary objectives are described separately for the core part and the extension part:

Core part

Assess the consistency of the efficacy of ofatumumab versus placebo across regions (Japan vs other countries) in the cumulative number of Gd-enhanced T1 lesions on MRI scans at Week 12, 16, 20 and 24. ([Section 2.5.4](#))

Assess the efficacy of ofatumumab versus placebo in the number of new or enlarging T2 lesions on MRI scans. ([Section 2.7](#))

Assess the efficacy of ofatumumab versus placebo in annualized relapse rate (ARR) and time to first relapse. ([Section 2.7](#))

Assess the safety and tolerability of ofatumumab versus placebo. ([Section 2.8](#))

Assess the similarity of the pharmacokinetics (PK) and B-cell count following the treatment with ofatumumab across regions (Japan vs other countries). ([Section 2.9](#), [Section 2.10](#), [Section 2.8](#))

[figure not shown]
Extension part (additional to objectives for Core part)

Assess extended safety and tolerability of ofatumumab. ([Section 2.8](#))

Assess extended efficacy of ofatumumab in:

- Number of Gd-enhanced T1 lesions ([Section 2.5](#))
- Number of new or enlarging T2 lesions ([Section 2.7](#))
- Annualized relapse rate ([Section 2.7](#))
- Time to first relapse ([Section 2.7](#))

Assess the PK and B-cell count following the extended treatment with ofatumumab. ([Section 2.9](#), [Section 2.10](#), [Section 2.8](#))

2 Statistical methods

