2.2 Analysis sets

Full analysis set (FAS): The FAS comprises all randomized subjects with assigned treatments. Subjects will be analyzed according to the randomized treatment assignment following the intention-to-treat (ITT) principle, even if they actually received no or a different treatment.

The FAS will be used for the summary of demography and baseline characteristics and all efficacy analyses.

Extension FAS (EFAS): The EFAS will include all FAS subjects who received at least one dose of ofatumumab during Extension part. Analyses on EFAS will include *all* available efficacy assessments of the Core and Extension parts.

Per-protocol set (PPS): The PPS is a subset of FAS, consists of all randomized subjects who take at least one dose of study medication and have no major protocol deviations that could confound the interpretation of analyses conducted on the FAS. Major protocol deviations will be determined according to the pre-defined protocol deviation criteria before treatment unblinding (e.g. non-compliance for a large proportion of the time in study). For analyses performed on the PPS, only on-treatment assessments will be used.

The PPS will primarily be used for the supportive analyses of the primary efficacy variable.

Safety set (SAF): The SAF set includes all subjects who received at least one dose of study medication. Subjects will be analyzed according to the actual treatment received. The Safety Set will be used for all safety analyses for Cut-off 1 analysis.

Extension Safety set (ESAF): The ESAF set includes all subjects who received at least one dose of ofatumumab during Extension part. Subjects will be analyzed according to the actual treatment received. The Extension Safety Set will be used for all Cut-off 2 and final safety analyses. Analyses on ESAF will include safety assessments *only under ofatumumab treatment during the Core and Extension parts*.

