2.10 PD and PK/PD analyses

PK concentration and B-cell count data will be summarized by visit for the overall population, and separately by region (Japan or non-Japan) and provided together with by-patient listings in the study report. All patients in FAS with non-missing values will be included in these analyses.

[figure not shown]

[figure not shown]

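### SAP 2.9 sets missing PK concentrations to zero and uses an undefined completer population, in conflict with SAP 2.10

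*SAP*

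**What the plan says.** SAP 2.9 (Pharmacokinetic endpoints) makes three statements.

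- Population: "All completed subjects will be included in the pharmacokinetic (PK) data analysis".
- Values: "Missing values or those below the limit of quantification (LOQ) will be indicated in the data listings and treated as zero". The zero applies both to what is displayed and to what is calculated.
- Statistics: PK parameters are "expressed as mean, SD, and CV, with geometric means will be summarized".

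SAP 2.10 (PD and PK/PD analyses) plans the summary of PK concentrations and B-cell counts by visit, overall and by region, as Protocol 9.5.4 does. Its population rule is: "All patients in FAS with non-missing values will be included in these analyses".

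Similarity of PK between Japan and the other countries is a secondary objective of the Core part (Protocol 2.1.2, SAP 1.2). SAP 1.2 refers that objective to Sections 2.9, 2.10 and 2.8 together and gives no order of precedence. The visible text of Protocol 9.5.4 names neither a PK population nor a rule for missing or below-LOQ values. SAP Section 4 lists neither PK rule as a change from the protocol.

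**The concern.** A result below the LOQ is information: the sample was assayed and the concentration was low. A missed, lost or unusable sample says nothing about the concentration. Giving both the same zero puts false low values into the calculation, so means fall and the CV rises with the number of samples lost, whatever the drug does.

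The two sections also disagree on who is analysed. One takes completers, without saying what was completed; the other takes FAS patients with non-missing values. Two programmers could each follow the SAP faithfully and produce different PK tables. The study is meant to support registration in Japan and PK similarity across regions is one of its objectives, so the rule should not be left to interpretation.

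**Working it through.** The documents give no PK sample size, variability, margin or missing-sample rate, so there is no figure of the plan's to reproduce. The check compares the texts and then works out what a zero does.

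**Comparison of the rules**

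| | SAP 2.9 | SAP 2.10 |
|---|---|---|
| Scope | PK data analysis, no exception stated | PK concentration and B-cell count, by visit, overall and by region |
| Population | Completed subjects | FAS |
| Missing values | Zero | Not included |
| Below LOQ | Zero | No separate rule |

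**Is the completer population defined?** SAP 2.2 defines FAS, EFAS, PPS, SAF and ESAF, and Table 5-5 classifies patients into FAS, PPS and SAF. None is a completer or PK set. The nearest definition is Protocol 5.6.1, where a patient completes the study on completing the EOS visit. Footnote 2 of Table 6-1 requires that visit of everyone, including patients who permanently stop study drug. At the Week 24 analysis, patients continuing in the Extension have not had an EOS visit, while those who stopped early and attended one have. Taken literally, the definition would admit the early stoppers and leave out the continuing patients, which cannot be intended. SAP 2.3.1 speaks of completion separately for the Core part, the open-label period and Safety FU, so it does not settle the matter.

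**Does 2.10 remove the zero rule from its own table?** Probably. However, patients with non-missing values could also mean patients with at least one value, and their missing visits would then still fall under 2.9.

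**Arithmetic where 2.9 is applied**

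Inputs: 60 patients randomized 2:1 give 40 on ofatumumab. With 30 of the 60 from Japan, that is about 20 on ofatumumab per region, or 18 after the 10% dropout allowance (SAP 3). The true CV is an assumption, shown for 30% to 80%.

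If a fraction p of values is set to zero:

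- mean as a share of the true mean = 1 − p
- apparent CV = √[(1 + CV²)/(1 − p) − 1]

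Mean: one zero in 20 lowers it by 1/20 = 5.0%; one in 18 by 1/18 = 5.6%; two in 20 by 2/20 = 10%.

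CV, worked once for a true 50% and p = 2/20: √[(1 + 0.25)/0.90 − 1] = √0.3889 = 62.4%.

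| Assumed true CV | 1 of 20 set to zero | 2 of 20 set to zero |
|---|---|---|
| 30% | 38.4% | 45.9% |
| 50% | 56.2% | 62.4% |
| 80% | 85.2% | 90.7% |

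Geometric mean: exp(mean of log x) does not exist if any x is 0, and the product form gives 0. One zero is enough.

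**The case against.** The strongest reply is that the regional objective is already protected. SAP 2.10 is the only visible section that plans PK by visit and by region, it mirrors Protocol 9.5.4, and it excludes missing values. A specific rule normally overrides a general one, and a list of cross-references in SAP 1.2 is ordinary indexing. This largely stands. What remains is that 2.9 is wrong for any other PK summary it controls, and that precedence has to be inferred.

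Three stronger readings are tempting, and the documents do not carry them.

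- A reader might infer that the regional comparison will be biased: with identical true PK, one sample lost against none gives a ratio of 19/20 = 0.95, and two against none gives 18/20 = 0.90. This applies the zero rule of 2.9 to the table of 2.10, which is the less natural reading. It also needs unequal loss; equal loss gives 1.00.
- A reader might infer that valid early samples from patients who stop will be discarded. That requires completion to mean completion of the Core part, which is only one possible meaning. The two faults also partly offset each other: if non-completers are left out, their later absent visits are not filled with zeros.
- A reader might infer frequent zeros from Protocol 3.3: "High number of PK values below the lower limit of quantification (LLQ) did not allow for use of a full PK/PD modeling". That concerns below-LLQ values, not missing samples, in a study with other doses and intervals. It makes below-LOQ handling worth specifying but gives no rate for this trial.

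The geometric-mean point is also conditional. Protocol 6.6.1 sends steady-state troughs to a population PK analysis, and no visible passage says that a summarised parameter is taken directly from zero-filled concentrations. Material near SAP 2.10 and Protocol 9.5.4 is not shown, so the point rests on visible sentences that conflict and not on something being absent.

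**Conclusion.** SAP 2.9 is wrong as written in treating missing PK values as zero, and its population is undefined and inconsistent with 2.10. Wherever 2.9 is applied to about 20 ofatumumab patients, each missing sample costs about 5% of the arithmetic mean, and an assumed CV of 50% becomes 62% with two zeros. A geometric mean over values that include a zero is zero or undefined.

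The sizes rest on the planned allocation with an even split between regions, on assumed CVs, and on assumed counts of lost samples. The consequence is limited. The visible regional comparison is descriptive, with no test or margin; missing and below-LOQ values are flagged in listings; population PK is planned; and 2.10, read naturally, already keeps missing values out of the regional summary. The documents do not support a claim that the regional PK result will be distorted.

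**What to change.** Four changes to the SAP text:

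1. In 2.9, take missing values out of the zero rule: flag them in listings and leave them missing. Keep a separate, stated rule for below-LOQ values; zero in arithmetic summaries is acceptable.
2. Replace the completer wording with ofatumumab-treated patients who have at least one valid PK concentration, and align 2.10 with it. The restriction to ofatumumab is needed because the FAS is all randomized patients and so includes the placebo arm. Say explicitly that a patient's missing visits stay missing.
3. State that 2.10 governs the by-visit, by-region summary for the regional PK objective.
4. Beside any geometric mean, show the number and percentage of values below LOQ, and pre-specify how those values enter it. The method is for the sponsor to choose. Using quantifiable values only is one option, but it drops the low values and could itself distort a regional comparison if below-LOQ rates differ.

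The cost is SAP wording and programming. Data collection and trial conduct do not change. If PK tables from an earlier cut-off already exist, check which rule produced them.
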